Evaluation of the Effects of Mandibular Advancement Device in Obstructive Sleep Apnea Patients

A research protocol

*Submitted to the Faculty of Dentistry, Ain Shams University in partial fulfillment
of the requirements of PHD in Orthodontics*

March 2020

Contents

- 1. Introduction**
- 2. Aim of the study**
- 3. Material and methods**
- 4. Data management**
- 5. Statistical analysis**
- 6. Ethical revision**
- 7. References**

Introduction

Sleep-related breathing disorders (SRBDs) constitute a diagnostic entity of disease that encompasses obstructive phenomena, including primary snoring, and Obstructive sleep apnea-hypopnea syndrome (OSAHS), along with the related disorders of central sleep apnea and sleep-related hypoventilation. [1]

Obstructive sleep apnea-hypopnea syndrome (OSAHS) is characterized by the occurrence of abnormally frequent episodes of partial (hypopnea) or complete obstruction (apnea) of the upper airway during sleep.[2]

The importance of addressing this disorder lies in the fact that it has significant medical, psychological, and social consequences.[3]

OSA can be a serious, even life-threatening disorder. Interrupted episodes of sleep result in excessive daytime sleepiness which, in turn, increases the risk of motor vehicle accidents and diminishes quality of life. The chronic decrease in oxygen saturation along with the heightened sympathetic activity result in increased risk of endothelial damage to the blood vessels. This in turn may lead to coronary artery disease, congestive heart failure, myocardial infarction, hypertension, stroke, cardiac arrhythmia, and sudden cardiac death.[1]

Prevalence:

OSA is commonly thought to involve 2% of middle-aged women and 4% of middle-aged men.[4] A higher prevalence rate was mentioned in another study, stating that 14% of men and 5% of women suffer from OSA.[1]

Pathogenesis:

OSA results from sleep related narrowing of the upper airway. Both anatomical and neuromuscular factors play a role in the increased collapsibility of the upper airway . [5]

The pharyngeal critical closing pressure (Pcrit) is the pressure at which the upper airway collapses. When the airway becomes constricted during sleep, respiratory effort increases to maintain airflow, accompanied by relative increase in serum

carbon dioxide (hypercarbia) and decrease in serum oxygen (hypoxemia). The increased work of breathing causes arousal from sleep, which in turn raises sympathetic neural activity, leading to increased heart rate and blood pressure and a tendency for cardiac arrhythmia. Arousal from sleep helps to increase the airway patency once again and resumes the normal airflow. However, when subjects return to sleep subsequently, the sleep-related upper airway collapsibility recurs.[1]

Risk factors:

Individuals with certain characteristics appear to be predisposed to OSA. Conditions that may be risk factors for the development of OSA in adults include obesity (body mass index [BMI] >30 kg/m), menopause, male sex, and increasing age.[1]

Etiology:

The etiology of OSA is multifactorial. Many factors related to the anatomical craniofacial structures and the neuromuscular tone are the main reasons. The most common predisposing craniofacial morphologies are retrognathia, dolichocephalic facial type, narrow and deep palate, steep mandibular plane angle, anterior open bite, midface deficiency, and lower hyoid position. Regarding the functional etiological factors, collapsibility of the upper airway is influenced by hormonal fluctuation (eg, pregnancy or menopause), obesity, rostral fluid shifts.,[1]

Diagnosis:

The gold standard for diagnostic confirmation of OSA is an in-center overnight sleep study (**polysomnography [PSG]**) or out-of-center sleep testing (OCST). Polysomnography is performed by a sleep medicine specialist. Home sleep apnea testing (HSAT) is a type of OCST. The overnight polysomnography includes at least 7 channels of recording, including electroencephalography (EEG), electrocardiography, and monitoring of sleep, airflow through the nose and mouth, pulse oximetry, respiratory effort, and leg movement. [1]

Two main indices are important for determining the severity of OSA. These are the respiratory disturbance index (RDI) and the apnea-hypopnea index (AHI). The respiratory disturbance index includes the number of apneas, hypopneas, and respiratory effort-related arousals RERAs per hour of sleep. The apnea-hypopnea index (AHI) includes the number of apneas and hypopneas per hour of sleep.[1]

Classification of OSA:

OSA can be categorized into mild (AHI or RDI >5 and <15), moderate (AHI or RDI >15 and <30), and severe (AHI or RDI >30).[1]

OSA lines of treatment:

1. Surgical treatment:

A common staged protocol involves utilizing uvulopalato-pharyngoplasty with tongue suspension or with genioglossus advancement and hyoid myotomy (Phase I) and maxillary and mandibular advancement osteotomy (Phase II). Several new techniques of upper airway surgical modifications have recently been described. Submucosal lingualplasty in combination with palatal surgery was found to be effective in improving sleep apnea symptoms.[6]

2. Non-Surgical treatment:

- A. Continuous Positive airway pressure (CPAP) therapy is the gold standard treatment for OSA in adults. CPAP acts as a high pressure splint that maintains patency of the upper airway. It is delivered through a mask interface.[5]
- B. Other treatment options include positional therapy (avoidance of sleeping on back) and body weight reduction. Drug therapy may be indicated for cases of nasal congestion or allergic rhinitis.[1]

C. Oral appliances:

Oral appliances are indicated, and may be a first-line therapy for patients with mild to moderate OSA and primary snoring. Oral appliances may also be a second line of therapy for patients with severe OSA who do not respond to or are unable or unwilling to tolerate positive airway pressure (PAP) therapies.[7]

Several studies have demonstrated that OAs and PAP therapy were comparable in improving daytime somnolence, hypertension, neurocognitive function, quality-of-life indices, and cardiovascular mortality.[6, 8]

The **Advantages** of oral appliances are silent, portable, noninvasive, and well tolerated. Most side effects tend to be transient, though permanent dental consequences may occur.[7]

Types of Oral appliances:

- i. The most commonly used oral appliances are the Mandibular Advancement Devices (**MADs**) which advance the mandible and the genio-glossus muscles thus enlarging the airway.[1]

- ii. **Tongue-stabilizing devices** may also be used in controlling mild to moderate OSA cases. Tongue-stabilizing devices use suction to protrude the tongue forward, however it is less tolerated than mandibular advancement devices[6] TDs are used in patients with large tongues, or when there are contraindications to use of an MRA. Some TDs are custom made for the patient (e.g., tongue retaining device (TRD) but some devices are prefabricated. To use the TRD the patient advances the tongue into the bulb while squeezing the bulb to create negative suction. The patient experiments with the amount of forward Positioning of the tongue that is required to decrease snoring and symptoms[9]
- iii. A third, less commonly used device is the **soft palate lifters**.

Regarding the Mandibular advancement devices (MADs), they may be **custom-made or ready-made**. Traditionally, MADs have been individually fabricated by a dental technician from plaster casts of patients' teeth and construction bites obtained by the dentist. Potential disadvantages of this custom-made method are the costs and time required to construct the device. Prefabricated MADs made of thermoplastic material, also called boil and bite appliances, could provide a reasonable alternative to custom-made devices to reduce the costs as well as the fabrication time. [10]

MADs may also be **dual-arch or monobloc**. In the Two-arch appliances, a locking mechanism is inserted to lock the appliance in a protruded position. Regarding the advancement mechanism of MADs, they may be constructed at a **single fixed protruded position, or they may be titrable**, having an adjustment screw to adjust the degree of advancement.[4] Custom, adjustable dual-arch OAs have been shown to be highly efficacious for treating primary snoring and mild-moderate OSA.[6]

The target degree of protrusion of the mandible is defined as the final and most effective protrusion, that yields the most successful outcome.[4] It varies from 50 to 75% of the maximum protrusion of the patient.[9]

Some studies have demonstrated a dose-dependent effect of mandibular advancement on OSA, i.e., more protrusion yielding larger improvements in OSA. However, an exaggerated mandibular protrusion can cause temporomandibular joint problems, and/or muscle discomfort. This suggests that the target protrusion is an individual variable for every patient.[4]

According to Ferguson et al, the most commonly used definition of success of MADs is a reduction to less than five respiratory events per hour of sleep while the

most liberal definition was a reduction of 50% or more from the baseline apnea-hypopnea index (AHI).[11]

Mehta and coworkers compared the patients' response to 2 devices, one that protruded the mandible and the other did not. The placebo device did not improve the AHI suggesting that it is protrusion that is necessary for the OA to be effective.[12]

Walker-Engström et al compared two different degrees of mandibular protrusion 50% or 75% of maximum using the same device in both groups. The success rate of the 75% protrusion proved to be higher than that of the 50% protrusion. Additionally, they did not find increased side effects with more protrusion.[13]

Therapeutic Mechanism of MADs:

The mandibular advancement device acts by displacing oropharyngeal tissues forward that results in a patent airway.[10]

According to **Haekema et al**, three different mechanisms may explain the efficacy of oral appliances in improving sleep respiration. First, mandibular advancement moves the suprathyroid and genioglossus muscles anteriorly, enlarging the airway, thus lessening the likelihood of its collapse. Second, downward movement of the mandible accompanies advancement, thereby exerting tension across the soft palate via the palatoglossal and palatopharyngeal arches, thereby preserving the velopharyngeal airway space. Third, the oral appliance maintains a forward position of the mandible and hyoid bone during sleep, preventing backward rotation of the jaw and retralapse of the tongue into the airway.[14]

Effects of MADs on airway dimensions:

Many imaging modalities were used for assessing the effects of MADs on the airway. Initially studies used two dimensional lateral cephalograms and demonstrated significant changes in the antero-posterior airway dimensions.[3] Later on, three dimensional studies using CBCT demonstrated an additional increase in transverse airway dimensions, which exceeded the increase in the anteroposterior dimension.[15]

Haskell et al used Cone beam Computed tomography to detect changes in airway volume caused by the mandibular advancement devices. They found that the largest changes occurred in the lateral rather than AP dimension, particularly at the level of the C2 vertebra; where the airway acquired a more elliptical cross-sectional shape.[16]

Shete and Bhad used a titrable twin block appliance and evaluated its effect on the airway using Cone beam computed tomography. They found greater

increases in transverse dimensions than in anteroposterior dimensions of the smallest cross sectional area in all patients irrespective of initial small or large transverse dimensions of the smallest cross section area. These findings are similar to those of Haskell et al.[15]

Zhao et al used Magnetic Resonance Imaging and demonstrated similar results.[17]

Side effects of MADs:

1. Effects on occlusion and alignment:

Tooth movement, specifically occlusal changes represented by incisor changes, position of canines, decreased overjet/overbite, and altered occlusal contacts/bite changes is a concern during the treatment of OSA using MADs.

Vranjes et al assessed the effect of a mandibular advancement device using scanned digital models. Eighteen patients were recruited in this study. They showed that a rigid MAD demonstrated no significant change in tooth position during the test period, or in bite changes per maximum intercuspal position, as measured by overjet and overbite. The mean change in Little Irregularity Index for the lower anterior teeth was 0.007 mm which was not statistically significant. Moreover, patients were highly satisfied with the device and considered it beneficial.[18]

A systematic review by **Araie et al** performed a meta-analysis on 12 studies to detect occlusal changes associated with MAD use. They demonstrated that MAD use was associated with a significant decrease of overjet (OJ) and overbite (OB), and it was suggested that both parameters decreased along with the duration of treatment. Meta-analysis also demonstrated a significant increase of L1-MP.

However, there were no significant changes of skeletal modifications or mandibular rotation. Changes of incisor inclination were suggested to make a contribution to reduction of OJ and OB. The mean decrease in overjet and overbite during the first year of use of MADs was 0.7 mm and 0.6 mm respectively. [19]

Fransson et al in 2020 conducted a 10-year prospective cephalometric study to evaluate the influence of a mandibular protruding device (MPD) in people with obstructive sleep apnea and snoring. At baseline and after 10 years, a lateral cephalogram was taken in the upright position. They showed that long-term nocturnal MPD use causes retroclination of the maxillary incisors and proclination of the mandibular incisors with consequent decreased overjet and overbite. Both MPD and MPD-stopped users obtained increased mandibular length and lower position of the hyoid bone, which can be a normal physiological change with age.[20]

2. Effects on Temporomandibular joint

Martinez-Gomis performed a study to assess Temporomandibular disorders (diagnosed according to the Research Diagnostic Criteria for TMD), overjet, overbite, occlusal contacts, subjective side effects, and technical complications before and after 14, 21, and 58 months of treatment using MADs. They found no significant variation in TMD prevalence. Subjective side effects were common, and a significant reduction was found in overjet, overbite, and in the number of occlusal contacts.[21]

A 2019 systematic review aimed to evaluate the effects of MADs on prevalence of TMD signs and symptoms in adult OSA patients. Twelve studies were included. The meta-regression analysis showed that patients with pre-existing signs and symptoms of TMD do not experience significant exacerbation of symptoms using the MAD. Moreover, the presence of TMD does not appear to be routine contraindication for the use of MAD used for the management of OSA.[22]

Orthodontists role in OSA management:

The orthodontist is involved in 2 main roles regarding OSA management:

1. Screening for obstructive sleep apnea (OSA). In the adult population, the Epworth Sleepiness Scale and Berlin and STOP-BANG questionnaires are examples of questionnaires that collectively focus on subjective and objective criteria and are valuable tools for the initial screening process.[23]

2. As part of the team involved in the multidisciplinary management of OSA in both children and adults.

Being experts in the science of facial growth and development, combined with their knowledge of mandibular advancing appliances , orthodontists are well suited to collaborate with physicians in the treatment of OSA.[1]

No clinical trials have been carried out previously to evaluate the effects and side effects three dimensionally on Egyptian population, thus came the idea of this study.

Aim of the study

The aim of this study is to investigate the effects of mandibular advancement device in obstructive sleep apnea patients.

Objectives:

The following parameters will be assessed:

- Respiratory sleep parameters.
- Occlusion (Inter-arch parameters)
- Dental parameters (Intra-arch parameters)
- Skeletal parameters
- Airway dimensions.

Material and Methods

This clinical study will be performed on ten patients referred from the outpatient clinics of Demerdash hospital, Ain Shams university.

The subjects will be selected to fulfill the following inclusion criteria:

1. Mild, moderate obstructive sleep apnea (OSA) as diagnosed on pre-treatment polysomnography. (measured by AHI or RDI) between 5 and 30 events per hour.
2. Age: adults aged above 18 years.
3. Sex: males and females
4. Subjects having a sufficient set of teeth to hold an appliance.
5. Subjects capable of giving informed consent.

Exclusion criteria:

1. Central sleep apnea.
2. Patients with severe periodontal disease
3. Patients with severe somatic or psychiatric disease
4. Pregnant females
5. Patients who are allergic to the appliance materials.

Methods:

Subjects in this study will receive a Mandibular advancement device (MAD).

The Mandibular advancement device that will be used in this study will be a custom-made, two-piece titrable appliance. The appliance consists of an upper and a lower compartment. Two acrylic flanges are constructed bilaterally on the buccal surface of the lower appliance in the molar region. These fit against a slot on the upper appliance in the same region, thus allowing engagement and locking of the

two appliances. The flanges are constructed at an angle to guide the mandible forward and maintain advancement. Two screw devices are incorporated posteriorly on each side in the upper appliance to enable advancement of the slots to permit incremental protrusion of the mandible.

Alginate impressions, as well as wax construction bites taken at 65% mandibular advancement will be taken to each patient for the purpose of appliance construction.

After appliance delivery, patients will be instructed to wear the appliance just before sleep and take it off in the morning after they wake up.

After acclimatization to wearing the appliance, the patients will be instructed to further advance the appliance by turning the screw forward two times per week (to achieve an advancement of 0.5 mm per week). Titration will be performed until subjects report improvement in their apnea symptoms, or until they cannot tolerate any further advancement.

Acclimatization to wearing the appliance will take 2 weeks, after which titration will be started.

The patients will be followed up on a weekly basis during the titration period, and then they will be followed up every 3 months for the rest of the study period.

Outcomes:

- Respiratory sleep parameters measured by Polysomnography.
- Occlusion (Overbite, overjet, molar relation) measured on digital study models.
- Dental parameters (incisors inclination, inter-molar width, inter-canine width, incisors irregularity, curve of spee) measured on digital study models and lateral cephalogram.
- Skeletal parameters measured on lateral cephalogram.
- Three-dimensional airway changes measured on Cone beam CT.

Measuring tools:

- Polysomnography test will be done before treatment and after 6 weeks of wearing the appliance (after titration is done) to detect improvement in respiratory sleep parameters.

- 3D Digital study models will be acquired for every patient before treatment and after one year of appliance use to detect changes in occlusion and alignment of teeth.
- Cone beam computed tomography scans will be taken before and after 6 weeks of wearing the appliance to measure three dimensional changes in airway. A lateral cephalogram will be derived from the pre-treatment CBCT.
- Lateral cephalogram will be taken after one year.
- Epworth sleepiness scale questionnaire will be used to evaluate the subjective improvement of OSA symptoms.

Data management:

All personal information about the participants will be confidential. Access to the final dataset will be limited to the investigators and the supervisors of this clinical trial.

Statistical Methods:

The study outcomes will be statistically analyzed to evaluate the changes brought by the appliance.

Informed consent and Adverse Event Reporting

Each participant will sign an informed consent describing in full details the interventions carried out in this clinical trial. Each participant has the right to withdraw from the study at any time without any penalty or loss of benefit.

Available data to the time of the participant's withdrawal might be included in the final data analysis.

Risks to Study Participants and Adverse Events Reporting:

Risks to study participants include temporomandibular joint symptoms and changes in occlusal relationship. Participants will be followed up for these side effects and will be managed accordingly.

Benefits to Study Participants and to the Community:

Benefits to the Study participants:

Treatment of OSA using oral appliances will improve the patients sleep which will in turn improve their quality of life. Also this will prevent the serious consequences of untreated OSA such as cardiac diseases, Diabetes, and Stroke. Moreover, day-time sleepiness will decrease with the consequent improvement in the patients' occupational performance.

Benefits to the Community:

Decreased day-time sleepiness will lead to better occupational performance, and more subjects' productivity. Also the decreased sleepiness may lead to decreased motor vehicle accidents.

References

1. Behrents, R.G., et al., *Obstructive sleep apnea and orthodontics: An American Association of Orthodontists White Paper*. Am J Orthod Dentofacial Orthop, 2019. **156**(1): p. 13-28.e1.
2. Vigie du Cayla, G., et al., *Long-term effectiveness and side effects of mandibular advancement devices on dental and skeletal parameters*. J Stomatol Oral Maxillofac Surg, 2019. **120**(1): p. 7-10.
3. Liu, Y., et al., *Effects of a mandibular repositioner on obstructive sleep apnea*. Am J Orthod Dentofacial Orthop, 2000. **118**(3): p. 248-56.
4. Dieltjens, M., et al., *Current opinions and clinical practice in the titration of oral appliances in the treatment of sleep-disordered breathing*. Sleep Med Rev, 2012. **16**(2): p. 177-85.
5. Cistulli, P.A., et al., *Treatment of snoring and obstructive sleep apnea with mandibular repositioning appliances*. Sleep Med Rev, 2004. **8**(6): p. 443-57.
6. Weaver, T.E., et al., *Innovative treatments for adults with obstructive sleep apnea*. Nature and science of sleep, 2014. **6**: p. 137-147.
7. Scherr, S., et al., *Definition of an Effective Oral Appliance for the Treatment of Obstructive Sleep Apnea and Snoring: A Report of the American Academy of Dental Sleep Medicine*. Journal of Dental Sleep Medicine, 2014. **1**.

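### Joint symptoms, discomfort, intolerance and device failure have no outcome, instrument or visit item, so the trial can report only structural side effects

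*Combined protocol and SAP*

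**What the plan says.** **Rationale and risks.** The last sentence of the Introduction justifies the study by the lack of earlier trials of effects and side effects, assessed in three dimensions, in an Egyptian population. The section on risks and adverse events reporting names joint symptoms and occlusal change, and says participants will be followed up and managed for them.

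**Background on side effects.** On oral appliances, the Introduction states: "Most side effects tend to be transient, though permanent dental consequences may occur". It also says that exaggerated protrusion can cause joint problems or muscle discomfort. Of a cited long-term study, which also assessed technical complications, it reports: "Subjective side effects were common, and a significant reduction was found in overjet, overbite, and in the number of occlusal contacts".

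**Outcomes and timing.** The Outcomes section lists polysomnography, occlusion, dental, skeletal and airway measures. For occlusion and tooth alignment, Measuring tools states: "3D Digital study models will be acquired for every patient before treatment and after one year of appliance use". The cephalogram has the same two time points, the first being derived from the pre-treatment CBCT. Polysomnography and CBCT are repeated at 6 weeks. The Epworth questionnaire is for improvement in apnea symptoms and has no stated time point.

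**Visits.** The Methods state: "Acclimatization to wearing the appliance will take 2 weeks, after which titration will be started". After that, "The patients will be followed up on a weekly basis during the titration period, and then they will be followed up every 3 months". No assessment is listed for these visits. On the end of titration: "Titration will be performed until subjects report improvement in their apnea symptoms, or until they cannot tolerate any further advancement".

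**The concern.** A study partly justified by side effects should be able to report the ones its own text expects. Here the harm-related outcomes are all structural. The background describes a wider picture in which most effects pass and some are symptoms rather than tooth movement. The risk section names a symptomatic risk, and the titration rule anticipates that some patients will reach a limit of tolerance. None of this has a defined route into the results.

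The loss would be permanent. A missing analysis can be written later from data that exist. A symptom that came and went between visits, with no form asking about it, cannot be reliably reconstructed at one year.

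**Working it through.** The plan states no side-effect rate and gives no sample-size calculation, so there is no planned figure to reproduce. The check maps each kind of side effect to the measure that could show it, then sizes the gap under stated assumptions.

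**1. What each measure can show**

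| Side effect | Measure in the plan | Time points |
|---|---|---|
| Overbite, overjet, molar relation | Study models | Baseline, one year |
| Arch widths, irregularity, curve of Spee, incisor inclination | Study models, cephalogram | Baseline, one year |
| Skeletal change | Cephalogram | Baseline, one year |
| Joint symptoms | Follow-up promised; no instrument, schedule, form or analysis | None stated |
| Muscle or other discomfort | None | None |
| Intolerance that ends titration | Acted on; no outcome reports it | None |
| Device breakage or loss | None | None |

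Polysomnography, CBCT and Epworth measure efficacy or the airway, so they fill none of the last four rows. Statistical Methods covers only the study outcomes, and none of those four rows is an outcome. The gap is therefore one of content as well as timing: models and a cephalogram would miss joint symptoms even if taken every week.

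**2. Contacts available**

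- Weekly visits: polysomnography at week 6, after titration, minus 2 weeks of acclimatization leaves 6 − 2 = 4 weeks, or about 4 visits.
- Three-monthly visits before week 52: weeks 13, 26 and 39 if counted from the start, or weeks 19, 32 and 45 if counted from week 6. Either way there are 3.
- Total: 4 + 3 = about 7 contacts before the one-year records.

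**3. Size of the gap (assumed rates)**

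The planned sample is 10 ("This clinical study will be performed on ten patients referred from the outpatient clinics"). Let p be the share of patients with a transient side effect at some time, and q the share of those still affected at one year. Both are assumptions.

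- Expected number ever affected = 10p.
- Chance that at least one patient is affected = 1 − (1 − p)^10.
- If a symptom check were made at one year only, the chance of seeing at least one = 1 − (1 − pq)^10.

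| p | Expected ever affected | Chance of at least one | One-year check only, q = 10% | One-year check only, q = 25% |
|---|---|---|---|---|
| 20% | 2 | 89% | 18% | 40% |
| 40% | 4 | 99% | 34% | 65% |
| 60% | 6 | >99.9% | 46% | 80% |

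The plan specifies no symptom check even at one year, so the last two columns flatter it. They show that adding one at one year alone would recover only part of the loss.

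**4. Precision if the data were collected**

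For 0 of 10, the exact two-sided 95% upper limit is 1 − 0.025^(1/10) = 30.8%. Exact (Clopper–Pearson) limits are 2.5% to 55.6% for 2 of 10, 12.2% to 73.8% for 4 of 10, and 26.2% to 87.8% for 6 of 10. This width comes from the sample size, not from the recording gap, and recording will not remove it.

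**The case against.** The strongest reply is that the plan does attend to side effects. The risk section commits to follow-up for joint symptoms and bite change and introduces its two risks as examples, not a complete list. Tolerance is also judged during titration. A reader might infer that nothing at all is recorded at the visits. The documents do not support that: they show that no item, instrument, schedule or analysis is specified. That much of the objection stands. But a promise to follow up and manage is a care commitment, and it gives no figure a route into the results.

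A reader might also infer that early discomfort is known to be common. It is not shown here. The cited study that found "Subjective side effects were common" made its on-treatment assessments at 14, 21 and 58 months. The muscle-discomfort remark concerns exaggerated protrusion, and another cited trial found no more side effects at 75% than at 50% protrusion. The documents give no early rate.

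Third, the rationale speaks of three-dimensional evaluation, the five objectives are respiratory or structural, and no overall tolerability claim is planned. So it cannot be said that the device will be reported as better tolerated than it was. Nor would the planned outcomes show 0 of 10 with discomfort: an unmeasured symptom is absent from the report, which differs from an observed zero. What remains is that a risk the plan itself names, joint symptoms, has no outcome at any time point.

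**Conclusion.** The gap is real and should be closed before enrolment. Followed as written, the trial can report only structural side effects, at one year. Joint symptoms, discomfort, intolerance and device failure have no defined measure at any of about 7 earlier contacts or at one year.

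The size of the loss is unknown. The figure of about 2 to 6 unreported patients out of 10 rests on an assumed 20% to 60% affected. The count of 7 contacts assumes that titration fills weeks 3 to 6 and that three-monthly visits are kept to one year. The finding concerns unspecified measurement; it makes no claim about how often these effects occur.

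**What to change.** Under Outcomes and Measuring tools, add a short fixed side-effect list, completed at baseline and at each weekly and three-monthly visit already planned, with onset and end dates. It should cover:

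- joint symptoms;
- muscle discomfort;
- titration stopped for intolerance;
- other problems the patient reports;
- device breakage or loss.

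At the first weekly visit, also ask about the 2-week acclimatization period, which precedes the weekly titration visits.

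Add a descriptive outcome: the number of patients with each side effect at any time, with exact 95% limits. The denominator should be all patients who received a device, including those who withdraw. This needs stating because the plan at present makes use of withdrawn patients' data optional, and patients who stop because of side effects could otherwise drop out of the count.

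The cost is one form, one table and a few minutes per visit, with no new procedure and no change to treatment. The downsides are some reliance on recall for the first two weeks, wide intervals with 10 patients, and a reported side-effect profile that may look less favourable.

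### One-year skeletal change appears to compare a CBCT-derived baseline cephalogram with a separately taken one, and no common scale or head position is stated

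*Combined protocol and SAP*

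**What the plan says.** The combined protocol and SAP assigns one tool to the skeletal objective. Under Outcomes it lists "Skeletal parameters measured on lateral cephalogram". The dental parameters, which include incisor inclination, are "measured on digital study models and lateral cephalogram", without saying which tool serves which parameter.

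The imaging schedule is under Measuring tools:

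- CBCT: "Cone beam computed tomography scans will be taken before and after 6 weeks of wearing the appliance".
- Baseline cephalogram: "A lateral cephalogram will be derived from the pre-treatment CBCT".
- Follow-up cephalogram: "Lateral cephalogram will be taken after one year".

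Material and Methods states "This clinical study will be performed on ten patients", all of whom receive the device. The whole of Statistical Methods is: "The study outcomes will be statistically analyzed to evaluate the changes brought by the appliance". For neither cephalogram does the plan give a scale, magnification, calibration step, projection or head position.

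**The concern.** In a one-group before-and-after comparison, the two measurements must be made on the same footing. Here the baseline image is reconstructed from a volume scan, while the follow-up image is apparently acquired separately. If the two differ systematically in magnification, projection or head position, that difference enters every patient's change score. No control arm cancels it, and a larger sample would not shrink it.

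At stake is one of the five stated objectives, the skeletal one, which has no second measuring tool. Incisor inclination is also exposed if it is read on the cephalogram. Overjet, overbite and molar relation (digital models), airway (CBCT at both times) and respiratory outcomes (polysomnography) are not affected.

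**Working it through.** **Step 1. The image pair, from Outcomes and Measuring tools.**

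| | Baseline | 6 weeks | One year |
|---|---|---|---|
| CBCT | yes | yes | none scheduled |
| Lateral cephalogram | derived from CBCT | none stated | taken; type not named |

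No scheduled CBCT could supply the one-year cephalogram, and the section uses *derived* for one image and *taken* for the other. Two image types is the natural reading, but it is an inference.

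**Step 2. What an offset does.**

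Observed mean change = true mean change + mean offset between image types.

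The standard error of the mean change falls with the number of patients; the offset does not. Its sign is unknown, so it could mimic a change or hide one.

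**Step 3. Which measures are exposed.** A uniform scale mismatch *m* on a distance *L* gives a false change of *m* × *L* and leaves angles unchanged. A projection or head-position difference can alter both distances and angles. The plan names no skeletal parameter, so the split between the two kinds is unknown.

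**Step 4. Sensitivity to a scale mismatch (linear distances only).** The plan has no power, SD, effect size or test to reproduce. Ten patients is from the plan. Every other input is assumed: *L* = 70 mm, no true change, paired t-test at two-sided 5%, SD of change 1.0 to 3.0 mm, and mismatch 0.1 to 1%, constant across patients.

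The probability of a significant result comes from the noncentral t distribution with 9 degrees of freedom (critical value 2.262) and noncentrality *m* × *L* × √10 / SD. For example, at 1% and SD 1.0 mm, the false change is 0.01 × 70 = 0.7 mm, the noncentrality is 0.7 × 3.162 / 1.0 = 2.21, and the probability is 0.506.

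| Mismatch | False change | SD 1.0 mm | SD 1.5 mm | SD 2.0 mm | SD 3.0 mm |
|---|---|---|---|---|---|
| 0% | 0 mm | 5% | 5% | 5% | 5% |
| 0.1% | 0.07 mm | 5% | 5% | 5% | 5% |
| 0.2% | 0.14 mm | 7% | 6% | 5% | 5% |
| 0.5% | 0.35 mm | 17% | 10% | 8% | 6% |
| 1% | 0.70 mm | 51% | 26% | 17% | 10% |

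**Step 5. Mismatch that varies between patients.** Suppose the mismatch averages 1% with an SD of 2 percentage points. It adds 0.02 × 70 = 1.4 mm of spread, and the total SD is √(SD² + 1.4²) = 1.72, 2.05, 2.44 and 3.31 mm. The rates at mean 1% become 21%, 16%, 13% and 9%. Variation adds noise and lowers the false-positive rate, but the mean shift of 0.7 mm stays.

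**The case against.** The strongest reply is that the problem is conditional twice over. The change of image type rests on the contrast between two verbs. Even if the types differ, nothing in the documents shows a difference in scale or projection, because the plan is silent on tracing altogether and does not say that calibration will be omitted. This stands, and it limits the claim. A reader might infer that the skeletal result is demonstrably biased, or that a false finding is likely. The documents support neither.

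The illustration also has limits. It assumes a linear distance, and if all the skeletal parameters are angles a uniform scale mismatch does nothing. No test or significance level is planned. The 51% needs the largest mismatch and the smallest SD in the table, with no variation between patients, while mismatches of 0.1 to 0.2% leave the rate close to 5%. All of this stands. The projection and head-position route, which could affect angles, is not quantified here and cannot be from the documents.

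Another reply is that ten patients without a control group could not attribute skeletal change to the device anyway. That is true, and the Introduction itself allows that increased mandibular length can be a normal change with age. But attribution is a separate limit. An image offset would distort even the descriptive change over the year.

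The Introduction cites a long-term study whose cephalograms were taken upright at both times. A reader might take that as this trial's head position, but it describes the cited study only.

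**Conclusion.** The concern holds in conditional form. As written, the plan most naturally changes the image type between the two time points of a single-arm comparison, and nothing in it corrects for that. Any systematic difference would go straight into the one-year skeletal change, in an unknown direction, and could not be told apart from true change. Scale affects linear distances only; projection or head position could also affect angles, including incisor inclination if that is read on the cephalogram.

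The documents give no way to find the size. The 5 to 51% range in the table is a sensitivity range under stated assumptions, not an estimate for this trial. The case for acting rests on the low cost of making the images comparable, not on those percentages. If the one-year image turns out to share the source and scale of the baseline, the scale problem disappears.

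**What to change.** In Measuring tools:

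1. State the type of the one-year image and a common head position for both images. If source and scale match the baseline, say so.
2. If the types differ, generate the CBCT-derived baseline cephalogram with the projection and magnification of the one-year image where the software allows.
3. At minimum, calibrate both images to true size before tracing, using a ruler or known magnification on the one-year image. Report linear skeletal distances only after this correction.
4. State as a limitation that residual projection, head-position and landmark differences remain confounded with time.

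The cost is protocol wording, some software work and the stated limitation, with no added radiograph or visit. The documents do not show whether the software can match the projection. True-size calibration alone corrects scale only, so angles would stay exposed to projection and head-position differences. The change makes the two images more comparable; it does not allow skeletal change to be attributed to the device.
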